7. ASSESSMENTS

Every effort should be made to ensure that the protocol required tests and procedures are completed as described. However it is anticipated that from time to time there may be circumstances, outside of the control of the investigator that may make it unfeasible to perform the test. In these cases the investigator will take all steps necessary to ensure the safety and well-being of the subject. When a protocol required test cannot be performed the investigator will document the reason for this and any corrective and preventive actions which he/she has taken to ensure that normal processes are adhered to as soon as possible. The sponsor study team will be informed of these incidents in a timely fashion.

7.1. Efficacy

Methods of measuring the efficacy of rivipansel in treating subjects hospitalized for acute VOC that will be used throughout the study are described in this section.

7.1.1. Readiness-for-Discharge Criteria

The primary endpoint is time to readiness-for-discharge, where readiness-for-discharge is met when all of the applicable 6 criteria are documented to have occurred – the criteria are to be assessed in relation to treatment for this VOC event and acute complication(s) directly related to this VOC event:

1. Only oral pain medication is required.
2. Acute complications related to VOC (such as ACS, stroke, priapism) have resolved to the extent that management can be in an outpatient setting, if applicable.
3. IV opioids have been discontinued.
4. IV hydration has been discontinued, if applicable.
5. IV antibiotics have been discontinued, if applicable.
6. RBC transfusion is no longer required for the treatment of this VOC, if applicable.

Refer to the current version of the Readiness-for Discharge Assessments guidance document for examples and further information.

All criteria will be assessed by a member of the study site staff who will complete the readiness-for-discharge questionnaire in the eClinRO web-based data capture system, and enter data in the eCRFs (as appropriate). Once criteria 1 and/or 2 are met, they must be confirmed by the Investigator or qualified designee in the eClinRO web-based data capture system. The Investigator or qualified designee should be deemed, according to the institution's standard of care, appropriately qualified to determine discharge readiness and could be a physician, nurse practitioner, physician assistant, or other medical personnel. To

clarify, if criteria 1 and/or 2 are determined to be met by a member of the study site staff other than the Investigator or qualified designee, then the Investigator or qualified designee must confirm that assessment in the eClinRO web-based data capture system prior to the time the next scheduled assessment is to be made, or the time the subject is discharged, whichever comes first. Confirmation in the eClinRO web-based data capture system will also be required if there is a reversal in subsequent assessments of criteria 1 or 2. The Investigator or qualified designee will be notified in real-time via the eClinRO system whenever criteria 3 through 6 are noted to have been met by the assessor in the system. Site-staff will ensure that relevant data corresponding to criteria 3 through 6 are entered into the eCRF in a timely manner based on the subject's medical records.

The readiness-for-discharge criteria will be assessed in all subjects at pre-defined intervals (and ad hoc as necessary) from the start time of the loading dose until discharge. Routine assessments are to be performed during "daytime hours" only (defined as 6:01am to 10:00pm). Assessments are not to be performed during "night-time hours" (defined as 10:01pm to 6:00am), unless it becomes apparent that the subject has become ready-for-discharge during the "night-time hours", in which case an ad hoc assessment should be undertaken. If all readiness-for-discharge criteria are confirmed to be met prior to the discharge order being issued, and there are no reversals of the readiness-for-discharge status, further evaluations are not required to be documented in the eClinRO system following the time of the discharge order. However, all subjects should be followed until they have left the hospital (i.e., even after the discharge order is issued) to ensure there are no subsequent updates required to the readiness-for-discharge evaluation in the eClinRO system.

The schedule of readiness-for-discharge assessments may be different for the day the study drug loading dose is administered than for subsequent days. The details around the difference in these schedules are as follows:

If a subject receives their loading dose during the "daytime hours", readiness-for-discharge assessments for that day will be performed every 4 (± 1) hours from the start time of the loading dose until 10:00pm. At 10:00pm (± 1 hour) an assessment will be performed, signaling the end of the "daytime hours" and the start of the "night-time hours". The next routine assessment will then be at 6:01am (± 1 hour) the following morning, signaling the start of the "daytime hours" for that day. The schedule will then be reset such that, further assessments will be performed at 4 (± 1) hourly intervals until 10:00pm (± 1 hour) that night and this schedule of assessments (6:01am, 10:00am, 2:00pm, 6:00pm and 10:00pm, each ± 1 hour) will continue for all subsequent days of Visit 1, until the subject is discharged from the hospital.

If a subject receives their loading dose during the "night-time hours" then the first routine assessment of readiness-for-discharge will be at 6:01am (± 1 hour) at the end of the "night-time hours" and the start of the "daytime hours". Further assessments will then be performed at 4 (± 1) hourly intervals until 10:00pm (± 1 hour) that night and this schedule of assessments (6:01am, 10:00am, 2:00pm, 6:00pm and 10:00pm,

each ± 1 hour) will continue for all subsequent days of Visit 1, until the subject is discharged from the hospital.

In addition, an assessment should always be made at the time the decision is made to discharge the subject, regardless of the hour.

If the subject is asleep during “daytime hours” and IV opioids have not yet been discontinued, the subject does not have to be woken to perform the assessment as this can be undertaken while the subject remains asleep. However, if IV opioids have been discontinued then it may be necessary to wake the subject to determine the answer to Question 1 (Only oral pain medication is required?).

The study site staff, including the investigator (or qualified designee), will use an electronic device (eg, smart phone, tablet, or computer) to access the eClinRO web-based data capture system to record and confirm responses to the criteria in the readiness-for-discharge questionnaire. Example screen shots of the readiness-for-discharge questionnaire are included in the eClinRO reference document.

If the study site staff attempts, but is unable to complete the readiness-for-discharge questionnaire in the eClinRO system, a back-up data capture method will be utilized as outlined in the Readiness-for-Discharge Assessments guidance document.

If a subject did not receive any IV hydration, IV antibiotics or RBC transfusions, or had no acute complications related to VOC, then these criteria will not affect the determination of the primary endpoint (ie, they are not applicable).

The derivation of the primary endpoint of time to readiness-for-discharge makes use of the dates and times when each of the individual criteria are met. In this derivation:

- For **criteria 1**, the earliest date and time of “yes” reported by assessor and confirmed by the Investigator or qualified designee after the last “no” response recorded in the eClinRO web-based data capture system will be used.

7.2. Safety

Safety will be assessed by physical examinations, vital signs, clinical laboratory results and the spontaneous reporting of AEs, in all subjects who sign consent/assent. Unscheduled safety assessments may be performed at any time during the study to assess any perceived safety concerns. Investigators and Pfizer Clinicians will review individual subject data throughout the conduct of the study to ensure subjects' well-being.

7.2.1. Physical Examination

A complete physical examination will be performed at the VOC/Treatment-Ready Screening visit (see [Table 1](#), Schedule of Activities). The following parameters and body systems will be assessed and any abnormalities described: general appearance, skin, head, ears, eyes, nose, mouth, throat, spine, neck, thyroid, chest, respiratory, cardiovascular, abdominal (including liver and kidneys), musculoskeletal, extremities, neurological, genitourinary and lymph nodes. Particular attention will be directed at areas affected by pain as well as to the respiratory system for clinical signs of ACS such as chest wall pain, tachypnea and wheezing or rales on chest auscultation and the genitourinary system for clinical signs of priapism.

A targeted physical examination will be performed daily while the subject is in the hospital through 24 hours after the last dose of study drug (if not discharged first), at discharge, and at Day 35 Post-Discharge Follow-Up visit (Visit 4) (see [Table 1](#) Schedule of Activities) assessing the following at a minimum: skin, chest, respiratory, cardiovascular, abdominal and musculoskeletal examinations. Particular attention will be directed at areas affected by pain. Additional body systems may be assessed at the discretion of the investigator.

7.2.2. Vital Signs

Temperature, respiratory rate, pulse, blood pressure, and pulse oximetry will be collected throughout the study at the VOC/Treatment-Ready Screening visit, daily while the subject is in the hospital, and at Day 35 Post-Discharge Follow-Up visit (Visit 4) (see [Table 1](#) Schedule of Activities).

Temperature will be collected as oral, tympanic, temporal, or axillary temperature measured in degrees Celsius. Sites are encouraged to use the same method throughout the study.

Blood pressure should be measured in the subject's dominant arm and recorded to the nearest mmHg. Sites are encouraged to use the same arm throughout the study. All blood pressure should be measured consistently throughout the study with the subject in a supine position or in a sitting position, depending on the subject's clinical status.

The use of automated devices for measuring blood pressure and pulse rate are acceptable, although, when done manually, pulse rate will be measured in the brachial/radial artery for at least 30 seconds. When the timing of these measurements coincides with a blood collection, blood pressure and pulse rate should be obtained first.

Weight is to be measured in kilograms.

Height is to be measured in centimeters and recorded to one decimal place using a stadiometer, if available. The height should be measured with the subject not wearing shoes. If necessary, height can be measured while subject is lying down.

Pulse oximetry will be measured with a pulse oximeter and reported as a percent (use of oxygen supplementation will also be recorded).

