2.2.2. Safety

- Incidence and severity of adverse events during study.
- Incidence of clinical laboratory abnormalities and change from baseline in clinical laboratory values at end of treatment.
- Incidence of clinically significant changes in physical examination.
- Change from baseline in vital signs over the study.
- Incidence of adjudicated ACS.
- Incidence of adjudicated severe and/or generalized cutaneous manifestations.
- Percent of subjects re-hospitalized for VOC within 7, 14 and 30 days of discharge.

090177e1915da01b\Approved\Approved On: 16-Jul-2019 18:44 (GMT)

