4.2. Exclusion Criteria

Subjects presenting with any of the following, from the time of VOC/Treatment-Ready Screening up to the time of randomization unless otherwise stated, will not be included in the study:

1. Serious systemic infection, evidenced by clinical signs and symptoms, and/or microbiological investigations, consistent with this diagnosis. Subjects with fever $< 39^{\circ}\text{C}$ (102.2°F) may be considered for enrollment if in the opinion of the investigator there is no evidence of any serious systemic infection. Subjects with fever $\geq 39^{\circ}\text{C}$ (102.2°F) are excluded.
2. Subjects presenting with the following clinical risk factors of acute chest syndrome:
 - Hypoxia – defined as O₂ saturation of $<90\%$ (by pulse oximetry) on room air on 2 separate readings 15 minutes apart, or single value of PaO₂ <60 mmHg on arterial blood gas,
and/or
 - Hemoglobin <5 gm/dL.

3. Acute chest syndrome, at the time of presentation, as defined by the National Institutes of Health (NIH) treatment guidelines:^{24,25}

New pulmonary infiltrate involving at least one complete lung segment consistent with the presence of alveolar consolidation, (excluding atelectasis) AND one or more of the following:

- Chest pain;
- Temperature $>38.5^{\circ}$ C;
- Tachypnea;
- Wheezing or rales;
- Cough.

4. SCD pain atypical of VOC, including hepatic or splenic sequestration, cholecystitis, or pneumonia.

5. At the time of presentation:

- acute stroke, or
- severe avascular necrosis of the hip/shoulder when the presenting pain is only in the affected hip/shoulder.

6. Estimated glomerular filtration rate (eGFR) ≤ 60 mL/min/1.73 m² (refer to [Appendix 1](#) for calculation).

7. History consistent with rapidly progressive decrease or decrement in renal function, in the opinion of the investigator.

8. Alanine aminotransferase (ALT/SGPT) >3 times the upper limit of normal (X ULN) (based on clinic laboratory normal range).

9. Platelets $<50,000/\text{mm}^3$.

10. Subjects currently receiving transdermal analgesics and/or the expectation that transdermal analgesics may be used during the study for treatment of this episode of VOC (see Section 5.8.2).

11. Recent (within the past 30 days) major surgery (see definition in [Section 4.3.2](#)), hospitalization for reasons other than VOC, documented serious infection requiring IV antibiotic treatment, or significant bleeding.

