7.2.4.2.1. Severe ACS (Withdraw from Study Drug Administration)

For the purposes of this protocol, severe acute chest syndrome is defined as an ACS diagnosis as above ([Section 7.2.4.2](#)), and the requirement for at least one of the following:

- ICU Transfer;
- Mechanical ventilation;
- Oxygen requirement of >50% FiO₂, or the use of high flow oxygen delivery system, or bilevel positive airway pressure (BiPAP) or continuous positive airway pressure (CPAP).

Subjects that develop severe ACS are to be terminated from study drug administration. Subjects that develop mild or moderate cases of ACS may continue to receive treatment with study drug.

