7. HANDLING OF MISSING VALUES

- Missing values for safety endpoints will not be imputed.
- For time to event and IV opioid use calculations, measurement begins from the start date and time of the first infusion (loading dose) of the study drug. If the start date and time of the first infusion of study drug (loading dose) are not available, including scenarios where the subject is randomized but not treated, the time of 12:00 (24-hr clock) on the randomization date, will be used (time of randomization is not collected as part of the study database).

- The time of discontinuation from study is not collected in the study database, therefore 23:59 (24-hr clock) on the date of discontinuation from study will be used, when the time of discontinuation from study is needed for the derivation of any endpoint.
- If the date of death is present, but the time of death is missing, 23:59 (24-hr clock) on the date of death will be used, when the time of death is needed in the derivation of any endpoint.

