8.5. Analysis of Safety Data

For Cohort 1 and Cohort 2 combined, Cohort 1 by age group and Cohort 2 alone based on the Safety Analysis Set, the safety data (eg, AEs, SAEs, vital signs, physical examinations, laboratory tests) will be summarized in accordance with CDISC and Pfizer Standards (CaPS). In addition, for Cohort 1 and Cohort 2 combined ONLY, a 3-tier approach described below will be used for summarizing AE data. Safety data that will be specifically summarized include:

- Adverse events:

[figure not shown]
The analyses of adverse events will make use of the 3-tiered approach described below for Cohort 1 and Cohort 2 combined ONLY. These analyses will be considered exploratory. Under the 3-tier approach, AEs are classified into one of three tiers with different analyses performed for different tiers.

- Tier-1 events: These are events that are pre-specified events of clinical importance and are maintained in the custom AE term list system (CAETeLiSt).
- Tier-2 events: These are events that are not tier-1 but are “common”. A MedDRA Preferred Term (PT) is defined as a Tier-2 event (“common” event) if there are at least 4 in any treatment group.
- Tier-3 events: These are events that are neither tier-1 nor tier-2 events. Tier-3 events will be reported with observed proportions by treatment group without comparative statistics.

For Tier-1 events, the unconditional exact method for 95% CI for risk difference and p-value proposed by Chan and Zhang (1999) will be used to compare rivipansel with placebo. For Tier-2 events, the normal approximation will be used for calculating the 95% CI for risk difference. There will be no adjustment for multiple comparisons or stratification factors in the analyses.

- Safety laboratory tests reported according to CDISC and Pfizer standards (CaPS). Shift tables summarizing the changes in laboratory test results from baseline will be presented (see Appendix [Section 10.3](#) for details on shift tables).
- Incidence of clinically significant changes in physical examination will be summarized using descriptive statistics.
- Change from baseline at End of Treatment and at the Day 35 Post-discharge Visit in vital signs (eg, blood pressure, heart rate, temperature, respiratory rate, and pulse oximetry) will be reported using descriptive statistics.
- Incidence of adjudicated AEs will be analyzed using the same approach as for Tier-1 events.

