10.2. Definition and Use of Visit Windows in Reporting

Statistical Analysis Plan B5201002 v5

Page 48 of 56

090177e19152273c\Approved\Approved On: 12-Jul-2019 12:42 (GMT)

Other Endpoints:

For other endpoints, such as physical examination and vital signs, the data will be analyzed and presented based on the CRF recorded study visit time point. If there is more than one record for the same subject at the same time point, the most clinically extreme value will be

used as the observation for that time point. All observations will, however, be included in the listings.

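### The planned pulse oximetry summary ignores recorded oxygen use, so it can mask a desaturation that was treated with oxygen

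*Protocol*

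**What the plan says.** **Collection.** Protocol 7.2.2: "Pulse oximetry will be measured with a pulse oximeter and reported as a percent (use of oxygen supplementation will also be recorded". It does not require post-baseline readings to be on room air.

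**Endpoint.** Protocol 2.2.2 lists, without reference to oxygen, "Change from baseline in vital signs over the study".

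**Analysis.** SAP 8.5 plans "Change from baseline at End of Treatment and at the Day 35 Post-discharge Visit in vital signs", and the bracketed list that follows ends "respiratory rate, and pulse oximetry) will be reported using descriptive statistics". No split by oxygen use is stated.

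**Data handling.** SAP 7: "Missing values for safety endpoints will not be imputed". SAP 10.2, for vital signs among others: "If there is more than one record for the same subject at the same time point, the most clinically extreme value will be" taken as the observation, with all observations kept in listings.

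**Oxygen status elsewhere in the protocol.** Exclusion 2 in Protocol 4.2 includes "Hypoxia – defined as O₂ saturation of $<90\%$ (by pulse oximetry) on room air on 2 separate readings 15 minutes apart". The severe ACS definition in Protocol 7.2.4.2.1 includes "Oxygen requirement of >50% FiO₂, or the use of high flow oxygen delivery system". Protocol 5.8.4 names supplemental oxygen among the supportive treatments that subjects may receive.

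**The concern.** A saturation reading cannot be interpreted without knowing whether the subject was breathing room air. The protocol accepts this at entry, where hypoxia is judged on room air, and it has oxygen use recorded with pulse oximetry. The visible analysis text then drops the distinction.

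On-oxygen readings are foreseeable at End of Treatment. Severe ACS, which can be defined by high oxygen or ventilatory support, stops study drug (Protocol 7.2.4.2.1), and End of Treatment vital signs are taken within 24 hours after the last dose (Protocol 6.2.3). Some of those readings may be taken on support.

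At stake is whether the table for a stated safety endpoint can be read at face value. If one arm had more subjects needing oxygen at End of Treatment, the mean change could look alike in both arms.

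**Working it through.** The plan states no figure for this point, so there is none to reproduce. The check follows the variable through the documents and then sizes the effect under assumed values.

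**1. Tracing pulse oximetry**
- Collected as a percent, with oxygen use recorded (Protocol 7.2.2).
- Reported as change from baseline at two time points (SAP 8.5).
- An on-oxygen reading is not a missing value, so the no-imputation rule in SAP 7 leaves it as it stands.
- The extreme-value rule in SAP 10.2 picks a low room-air reading only if it is a second record at the same time point. It does not use oxygen status.
- No visible step connects recorded oxygen use to the summary.

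**2. One subject (assumed values)**

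Baseline is 95% on room air. At End of Treatment the room-air value would be 85% to 90%, a change of 85 − 95 = −10 to 90 − 95 = −5. The reading is actually taken on oxygen:

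| Reading on oxygen | Change reported | Room-air change |
|---|---|---|
| 93% | 93 − 95 = −2 | −10 to −5 |
| 95% | 95 − 95 = 0 | −10 to −5 |
| 98% | 98 − 95 = +3 | −10 to −5 |

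The outcome depends on the response to oxygen: a reduced fall, no change or an improvement.

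**3. Arm means (assumed values)**

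Let *d* be the excess proportion on oxygen at End of Treatment in one arm, *b* the room-air baseline, *r* the value that affected subjects would show on room air, and *o* their reading on oxygen. All other subjects are taken as unchanged.

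- Room-air difference in mean change = *d* × (*r* − *b*)
- Reported difference = *d* × (*o* − *b*)
- Hidden difference = *d* × (*o* − *r*), in which the baseline cancels

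With *b* = 96, *r* = 87 and *o* = 97:

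| Excess on oxygen | Room air | Reported | Hidden |
|---|---|---|---|
| 10 points | 0.10 × (−9) = −0.90 | 0.10 × 1 = +0.10 | 0.10 × 10 = 1.0 |
| 5 points | 0.05 × (−9) = −0.45 | 0.05 × 1 = +0.05 | 0.05 × 10 = 0.5 |

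Using the values in step 2, *o* − *r* runs from 93 − 90 = 3 to 98 − 85 = 13. The hidden difference then ranges from 0.3 to 1.3 points for a 10-point excess and from 0.15 to 0.65 for a 5-point excess.

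**4. The opposite direction (assumed values)**

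A subject reads 98% on oxygen at baseline, where room air would give 90%, and later reads 95% on room air. The reported change is 95 − 98 = −3. On room air it is 95 − 90 = +5.

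**5. Would restricting to room-air pairs repair it?**

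No. Under the assumptions of step 3 this removes every affected subject. The remaining subjects are unchanged in both arms, so the difference is 0 instead of −0.90. A count of subjects on oxygen or below 90% on room air would show the 10-point excess directly.

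**The case against.** **Other routes capture the event.** Adjudicated ACS is a separate safety endpoint. Oximetry is among the documents sent for adjudication (Protocol 7.2.4.2), and incidence is compared by exact methods (Protocol 9.4). An abnormal finding that needs intervention is reportable as an adverse event (Protocol 8.5), and common terms receive a risk-difference interval (SAP 8.5). This stands and limits the point. A reader might infer that the trial cannot detect an excess of hypoxia, or that severe ACS would go unseen. The documents do not support that. These routes do not correct the oximetry table, however: ACS requires a new infiltrate, so hypoxia without one falls outside that endpoint.

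**Exposure is narrow.** Dosing stops when only oral pain medication is required or after 15 doses, so for many subjects End of Treatment falls near recovery. Day 35 is postponed until an acute event has resolved (Protocol 6.4.3). This also stands. Masking needs a room-air baseline, oxygen still in use at End of Treatment and a response to it. A reader might infer that every treated desaturation is reported as unchanged or improved, but a partial response still shows a fall. Nor does exclusion 2 establish that the baseline vital sign was taken on room air, and Protocol 5.8.4 presents oxygen as care that may be given, not as care that is urged. An earlier in-hospital desaturation is missed for a different reason: the daily readings are not in this summary.

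**A rule may exist out of sight.** Safety summaries follow the sponsor's reporting standards, which are not shown, and parts of SAP 10.2 are blacked out. This is possible. If so, a cross-reference in SAP 8.5 would settle the matter.

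**Conclusion.** The point holds at minor severity. Oxygen use is recorded, the stated summary of pulse oximetry does not use it, and that summary can understate, cancel or reverse a treated desaturation, or exaggerate a decline in a subject who was on oxygen at baseline.

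The size rests wholly on assumed saturations and oxygen-use rates: about 1.0 point of mean difference hidden for a 10-percentage-point excess in oxygen use, and 0.5 for a 5-point excess, if 87% on room air is read as 97% on oxygen. The reported differences in that illustration (+0.10 and +0.05) are close to zero. The risk is mainly that a difference disappears, less that harm appears as benefit.

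The consequence is limited to one descriptive safety table. The primary analysis, alpha and power are unaffected.

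**What to change.** In SAP 8.5:

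- Present pulse oximetry values and change from baseline by recorded oxygen status (room air or supplemental oxygen) at baseline and at each reported time point.
- Give, by arm and time point, the number and percent of subjects on supplemental oxygen or below 90% on room air, as descriptive statistics. Label this as a single reading, since exclusion 2 requires two readings 15 minutes apart.
- Do not rely on an analysis restricted to room-air pairs. It leaves out the subjects who desaturated and were treated, and it selects on a state arising after randomisation.

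The cost is a short addition to the SAP text and one extra table from data the protocol already collects. Subgroups by oxygen status will be smaller, so their means will be less precise. SAP 1 states that the study team has remained blinded, so the change can be made before unblinding.
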